### **6.6.3 COVID-19 Listings**

A by-subject listing of COVID-19 impact codes by visit displays visits with abbreviated labels (e.g., SCR=Screening in pre-LTT, W12=Week 12 in LTT; FU2=Follow-up Week 2) in separate columns for the enrolled analysis set. Spanning headers above the visits display the analysis period (pre-LTT, LTT, or follow-up). Each column denotes an analysis visit in [Table 3](#) and displays the COVID-19 visit impact code (see Section [9.1.5.1](#)). If a subject has multiple COVID-19 visit impact codes in an analysis visit window, then results are displayed sorted by visit date and comma-concatenated across all COVID-19 visit dates in the analysis visit window (e.g., “#,&UM1” if “#” has visit date of 01JUL2020 and “&UM1” has visit date of 10JUL2020). Visits during the on-treatment safety analysis period are identified. Footnotes describe the abbreviations in the COVID-19 visit impact code (see Section [9.1.5.2](#)).

A by-subject listing of COVID-19 visit impact is provided for the enrolled analysis set (see Section [9.1.1](#)). The listing displays analysis period, analysis visit, COVID-19 visit date, study day derived from COVID-19 visit date, treatment day derived from COVID-19 visit date, visit type (scheduled or unscheduled), visit impact type, visit impact characteristics, visit impact relationship with specify text, and premature study termination (yes; no; not applicable).

## **7 CONVENTIONS**

### **7.1 Derived Dates**

Derived dates for defining analysis periods are defined as follows:

- Study drug date/time: Complete finding date/time corresponding to “yes” response to question about taking study medication and number of sprays  $> 0$  in the eDiary evening report or medication reconciliation form.
- Study drug start date/time: Earliest study drug date/time.
- Study drug end date/time: Latest study drug date/time.
- Study drug last date/time: Study drug end date/time derived only for subjects with non-missing response to the question “Did the subject complete the study?” on the Study Exit Status CRF. Thus, in an interim analysis, all post-baseline data are included for a subject who is still on study. At the last database lock, the study drug last date is equal to the study drug end date.
- LTT start date/time: Earlier of (1) study drug start date/time, and (2) IWRS baseline visit date (i.e., Baseline/Day 1 visit date from the BHV3500\_202 IWRS Visit Report csv file).
- LTT end date/time: Later of (1) latest complete finding date/time in the eDiary on or after the LTT start date/time, and (2) latest complete visit date on or after the LTT start date through the Week 52/Early Termination visit date, and excluding the Follow-up Week 2 visit date, from the Visit Date CRFs.

- LTT last date/time: LTT end date/time derived only for subjects with non-missing response to the question “Did the subject complete the study?” on the Study Exit Status CRF. Thus, in an interim analysis, all LTT data are included for a subject who is still on study. At the last database lock, the LTT last date is equal to the LTT end date.
- OP start date/time: Earliest complete finding date/time in the eDiary before the LTT start date/time.
- OP end date/time: Latest complete finding date/time in the eDiary before the LTT start date/time.
- COVID-19 visit date: (1) Complete visit date, if it exists; (2) otherwise, complete date the visit was planned to occur for a missed visit (see Section 9.1.1).
- Last contact date: (1) Earliest complete death date from the AE CRF, if it exists; (2) otherwise, the maximum complete date of the following: AE start or stop; COVID-19 visit only for in-person or remote visits; ECG; eDiary finding; informed consent; IWRS baseline visit; laboratory test collection; nasal inspection; non-study medication start or stop; physical exam; physical measurement; procedure; rating scale; questionnaire; vital sign; visit. If the last contact date is after the most recent raw database creation date, then it is set to the most recent raw database creation date.
- Death date: Last contact date derived only for subjects who died (see Section 6.4.1).

No imputations are performed on these derived dates. Complete dates are those with valid, non-missing day, month, and year.

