4.3.5 End of Treatment (early discontinuation or Week 52)

Subjects will return to the study site at Week 52, or at End of Treatment for those subjects who discontinue early, for review of the electronic evening reports, assessment of study drug compliance, and end of treatment procedures (Table 1). The POM and SM will be completed electronically and the MSQ, S-STS, MIDAS, and CGI-c will be completed on paper. Subjects must return all used and unused study drug and the provisioned electronic eCOA handheld device (if applicable) to the study site. This visit must be conducted in person, but may be delayed if necessary due to local COVID-19 safety requirements).

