4.3.6 Follow up Safety Visit

Subjects will return to the study site approximately 14 days after the Week 52/End of Treatment visit for a follow up safety visit and applicable study procedures (Table 1). Subjects will return the concomitant medication log at this visit for one final review by the study site staff. This visit must be conducted in person, but may be delayed if necessary due to local COVID-19 safety requirements).

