4.3.6.1 Electronic Data Collection

Subjects will complete electronic evening reports daily. The subjects may choose to either receive a provisioned device (referred to as an eCOA handheld device, or eDiary), or use their own smartphone device and download an application to report the evening reports. Subjects will also have access to a back-up method of reporting the electronic evening reports on a password

protected website. The website should be considered a backup method for completion of the electronic evening reports.

The following data will be reported by the subjects electronically throughout the study:

- Whether or not a migraine occurred
- Migraine pain intensity (mild, moderate, or severe)
- During the observation phase, if the migraine was treated with migraine standard of care medication
- During the long-term treatment phase, if the migraine was treated with study drug and nostril of administration (left or right)
- At the end of treatment visit, the PoM and SM.

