#### 6.4.6.2 *Treated Migraine Days per Month*

The number of treated migraine days per month is derived as follows:

- Month during LTT:
  - If the total number of study days in the month < 14: total number of treated migraine days in the month (i.e., no proration)
  - If the total number of study days in the month  $\geq 14$ :  $28 \times (\text{total number of treated migraine days in the month}) / (\text{total number of study days in the month})$
- Overall LTT:
  - If the total number of study days in the LTT analysis period < 14: total number of treated migraine days in the LTT analysis period (i.e., no proration)
  - If the total number of study days in the LTT analysis period  $\geq 14$ :  $28 \times (\text{total number of treated migraine days in the LTT analysis period}) / (\text{total number of study days in the LTT analysis period})$ .

All study days from LTT start to LTT end are included in analyses, not only days of data.

The following tables are produced for the safety analysis set:

- Number and percentage of subjects in the following categories based on the number of treated migraine days per month in the overall LTT by migraine intensity (total; moderate or severe): 0,  $> 0$  to  $< 1$ ,  $\geq 1$  to  $< 2$ ,  $\geq 2$  to  $< 3$ ,  $\geq 3$  to  $< 4$ ,  $\geq 4$  to  $< 5$ ,  $\geq 5$  to  $< 6$ ,  $\geq 6$  to  $< 7$ ,  $\geq 7$  to  $< 8$ ,  $\geq 8$ ,  $< 2$ ,  $\geq 2$ . The last 2 categories for total migraine intensity align with subgroups specified in Section 4.3.
- Number and percentage of subjects in the above categories based on the maximum number of treated migraine days per month in any 1 month during LTT by migraine intensity.

These tables are also produced for the safety analysis set with  $\geq 51$  weeks in the LTT analysis period (see Section 6.2.6.1).

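### SAP 7.1 caps the end of LTT at the Week 52/Early Termination visit for visit dates but not for eDiary dates, so a diary record after that visit stretches LTT into follow-up (minor)

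*SAP*

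**What the plan says.** SAP 7.1 takes the later of two dates as LTT end.

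- The eDiary limb is the "Later of (1) latest complete finding date/time in the eDiary on or after the LTT start date/time". It has a lower bound and no upper bound.
- The visit limb runs "through the Week 52/Early Termination visit date, and excluding the Follow-up Week 2 visit date, from the Visit Date CRFs". It stops at EOT.

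The LTT last date inherits the result: "At the last database lock, the LTT last date is equal to the LTT end date". No other SAP section cuts eDiary dates off at EOT.

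Protocol 4.3.5 says of the EOT visit: "Subjects must return all used and unused study drug and the provisioned electronic eCOA handheld device (if applicable) to the study site". Protocol 4.3.6 adds: "Subjects will return to the study site approximately 14 days after the Week 52/End of Treatment visit for a follow up safety visit"; Table 1 allows 2 days either side. Protocol 4.3.6.1 lets subjects report on their own smartphone, with a website as back-up, and introduces its list of items with "The following data will be reported by the subjects electronically throughout the study". No text closes the phone application or the website at EOT.

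LTT end then feeds:

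- time in LTT and average sprays per month (SAP 6.2.6.1);
- diary compliance (SAP 6.2.6.2);
- migraine days and treated migraine days (SAP 6.4.6), the latter with the statement "All study days from LTT start to LTT end are included in analyses, not only days of data";
- the visit windows (SAP 7.3).

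**The concern.** The visit limb shows the intent: LTT closes at EOT and the follow-up visit lies outside it. Because the later date wins, one complete eDiary record after EOT overrides that cap. By SAP 6.2.6.2, eDiary records include the evening report, the preference and satisfaction scales, and the site's medication reconciliation form.

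The days added are nominally off drug, since drug is to be returned at EOT. They enter every denominator that counts calendar days to LTT end. Two of the resulting rates define safety subgroups in SAP 4.3: average sprays per month (< 6, ≥ 6) and total treated migraine days per month (< 2, ≥ 2). AE and laboratory tables are repeated by these subgroups. A third quantity, diary compliance below 80%, is a relevant protocol deviation in SAP 9.2. The relative effect is largest in subjects who leave early.

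**Working it through.** The plan states no figure that depends on this rule, so there is nothing to reproduce. The check applies the SAP's own formulas with LTT ending at EOT and again with LTT ending at a later diary entry.

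**Inputs.** L = days of LTT when it ends at EOT. d = days from EOT to the last eDiary record. A last record at the follow-up visit gives d = 14, or 12 to 16 with the visit window.

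**Rates over calendar days.** For LTT of at least 2 weeks, average sprays per month = 4 × cumulative sprays / weeks in LTT. Overall treated migraine days per month = 28 × treated migraine days / study days in LTT, once there are 14 study days. With an unchanged numerator, each falls by d/(L+d):

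| L (days) | d = 2 | d = 12 | d = 14 | d = 16 |
|---|---|---|---|---|
| 28 | 6.7% | 30.0% | 33.3% | 36.4% |
| 84 | 2.3% | 12.5% | 14.3% | 16.0% |
| 126 | 1.6% | 8.7% | 10.0% | 11.3% |
| 168 | 1.2% | 6.7% | 7.7% | 8.7% |
| 364 | 0.5% | 3.2% | 3.7% | 4.2% |

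**Subgroup cut-points, d = 14.**

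- 78 sprays in 364 days (52 weeks): 4 × 78/52 = 6.00. In 378 days (54 weeks): 4 × 78/54 = 5.78. The subject moves from ≥ 6 to < 6.
- To stay at ≥ 6, the rate to EOT must be at least 6 × 378/364 = 6.23 at L = 364, or 6 × 98/84 = 7.00 at L = 84.
- 26 treated migraine days in 364 days: 28 × 26/364 = 2.00. In 378 days: 28 × 26/378 = 1.93. The subject moves from ≥ 2 to < 2.

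**Time in LTT.** The ≥ 51-week category needs 357 days. An EOT on day 343 (week 49) plus 14 days reaches it.

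**Diary compliance.** This is data days divided by calendar days from LTT start to end. With one stray entry at d = 14, 82% over 364 days becomes (0.82 × 364 + 1)/378 = 79.2%, and 85% over 84 days becomes (0.85 × 84 + 1)/98 = 73.9%. Both are now below 80%. Compliance falls only when few of the added days carry a report.

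**Migraine-day rate.** SAP 6.4.6.1 divides by data days. One stray report adds one day to the denominator, not 14, and adds to the numerator if a migraine is reported.

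**Visit label.** If a diary entry falls on or after the follow-up visit, that visit lies inside LTT. With EOT on day 358 and the visit on day 372, it falls in the Week 52 window (351 to 378). With EOT on day 365 and the visit on day 379, it falls in Extension.

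**The case against.** The strongest reply is that the trigger is off schedule. Table 1 marks no migraine report at the follow-up visit. The evening reports are last reviewed at EOT, and a provisioned device is handed back there. This stands as a limit on frequency: the share of affected subjects is unknown and may be zero. It does not make the rule right, because personal phones and the website are not stated to close.

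Three stronger readings are tempting, and the documents do not support them.

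- **That the safety results are contaminated.** SAP 7.2 sets the on-treatment and follow-up safety periods from the study drug last date plus 7 days. AE, SAE, discontinuation and laboratory classification therefore does not use LTT end. Time on zavegepant and patient-years use study drug dates. Even a relabelled follow-up visit keeps its safety period, which SAP 6.4 assigns in a separate step.
- **That the migraine-day results are diluted by the same factor.** They are not, because their denominator is data days. SAP 3.2 also gives this objective a treatment policy strategy, so including reports after drug discontinuation is not clearly an error.
- **That anyone leaving by day 126 has a bias of at least 10%.** With the nominal 14-day follow-up, that needs a last entry a full 14 days after EOT. At d = 2 it is 1.6%.

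A further objection concerns the remedy. Cumulative sprays sum every record with a complete study drug date, with no cap. Capping LTT end at EOT alone could keep a spray taken after EOT in the numerator while dropping its days from the denominator. SAP 6.2.6.2 tabulates subjects who do not return kits, so this is not idle. The objection stands and shapes the fix.

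**Conclusion.** The asymmetry is real, and following SAP 7.1 as written misdates LTT end for any subject with an eDiary record after EOT. For those subjects:

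- time in LTT is too long;
- average sprays and overall treated migraine days per month are too low, by d/(L+d);
- diary compliance can drop below 80%;
- the follow-up visit can be labelled as an LTT visit.

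The rate reductions assume at least 14 days of LTT to EOT and no study drug after EOT. The larger figures also assume a last entry at about the follow-up visit. A 52-week completer loses at most about 4%, and changes spray subgroup at d = 14 only if the rate to EOT lies between 6.00 and 6.23. Entry to the ≥ 51-week set concerns early leavers with EOT at weeks 49 to 51, since a Week 52 visit within its 7-day window already qualifies.

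Severity is minor: the effect is on descriptive and exploratory outputs and on AE subgroup assignment.

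**What to change.** Amend SAP 7.1. Where a Week 52/Early Termination visit date exists, set LTT end to the later of that visit date and the study drug end date, and let no other eDiary record after that date extend it. Where no such visit exists, keep the latest eDiary date as now. Using the study drug end date keeps any dose recorded after EOT and its days on the same side of the boundary.

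The cost is one clause and a small change to the derivation code, with no new data. If no records after EOT exist, no result changes. The amendment does not remove off-drug time before EOT, which can arise because Protocol 4.3.5 lets that visit be delayed.

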## 7.2 Analysis Periods

Analysis periods are defined as follows:

- OP: measurement date/time on or after the OP start date/time through the OP end date/time. This period is used to assess the number of migraine days per month during the OP.
- Pre-treatment: measurement date/time on or before the study drug start date/time. This period is used to derive baseline values, and to assess safety and outcomes research endpoints. Note that all measurements are pre-treatment for subjects in the enrolled analysis set with missing study drug start date.
- Pre-LTT: measurement date/time on or before the LTT start date/time. This period is used to derive analysis visit windows for slotting observations. Note that all measurements are pre-LTT for subjects in the enrolled analysis set with missing LTT start date.
- LTT: measurement date/time after the LTT start date/time through the LTT last date. This period is used to derive analysis visit windows for slotting observations, and to assess exposure and migraine days during LTT. Note that AEs with imputed start date equal to the

LTT start date are part of this period (refer to the Zavegeptan Core SAP for AE start date imputation).

- Follow-up: measurement date after the LTT last date. This period is used to slot observations.
- On-treatment safety: measurement date/time after the study drug start date/time through the study drug last date + 7 days. This period is used to assess safety endpoints on treatment.  
Note that AEs with imputed start date equal to the study drug start date are part of this period.
- Follow-up safety: measurement date after the study drug last date + 7 days. This period is used to assess safety endpoints during follow-up.

See Section 7.1 for derived dates for determining analysis periods. If measurement time is missing, not collected, or not applicable for a parameter, then the measurement date is compared to the derived date.

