	The screening phase includes a screening visit and a 28-day Observation Phase. Upon completion of the screening visit, subjects will electronically

[figure not shown]
record migraine occurrence every day. If a migraine occurs, subjects record migraine intensity and whether the migraine was treated. Subjects will report all concomitant medications, including migraine standard of care medications, in a concomitant medication log.

During the 28-day observation phase, the subject will return to the clinic for the pre-baseline visit. At the pre-baseline visit, a blood sample for laboratory tests will be collected.

After the pre-baseline visit, subjects will return to the clinic for the baseline visit. At the baseline visit, eligibility for continued participation in the study will be assessed. After the investigator reviews the results of the pre-baseline laboratory assessments and all other eligibility criteria, eligible subjects may be dispensed study drug and may start dosing in the long-term treatment phase. If eligible for the long-term treatment phase, subjects will be instructed that they can take study drug at the onset of a migraine. Subjects will be instructed that they can treat a maximum of 8 migraines per month (28 days) during the long-term treatment phase and that only one administration of study drug is allowed per calendar day. Subjects are required to continue to electronically record their migraine occurrence and migraine intensity daily. If the subject administers study drug to treat a migraine, the dose of study drug must also be reported on that day. Subjects will continue to record any concomitant medication use (including migraine standard of care medications) in the paper diary throughout the course of the study.

Subjects will have study visits at Week 2, Week 4 and every 4 weeks through Week 52. The Week 52 (+/- 7 days) visit is the end of treatment visit. There is a follow up visit 14 days (+/- 2 days) after the Week 52/end of treatment visit (see Table 1).

STUDY SCHEMATIC

Total study duration approximately 58 weeks

TABLE OF CONTENTS

1 IN	TRODUCTION AND RATIONALE	.14
1.1	THERAPEUTIC AREA BACKGROUND	.14
1.2	PRODUCT DEVELOPMENT BACKGROUND	.15
1.2.1	NON-CLINICAL PHARMACOLOGY	.15
1.2.1.1	NONCLINICAL PHARMACOKINETICS, PHARMACODYNAMICS,	
	AND TOXICOLOGY	.15
1.2.2	CLINICAL EXPERIENCE	.15
1.2.2.1		
1.2.2.2		
1.2.3	OTHER CLINICAL / NON-CLINICAL STUDIES	
1.2.3.1	PHASE 1 STUDIES	.16
1.2.4	CLINICAL ADVERSE EVENT PROFILE	.16
1.2.4.1		

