#### 6.4.2 Laboratory Tests

Laboratory tests are analyzed using results from the external central laboratory **CCI** [REDACTED] which identifies expired kits, and from local laboratory tests reported on CRFs. The central laboratory reports both laboratory collection date and time, whereas CRFs capture only laboratory collection date.

Laboratory tests of clinical interest are collected at the following visits:

- Hematology: Screening; Pre-Baseline; Weeks 4, 24, and 52; and early termination.
- Serum chemistry (including LFTs and lipids): Screening; Pre-Baseline; Weeks 4, 24, and 52; and early termination. Exceptions are for the following:
  - LFTs (ALT, AST, ALP, TBL, direct bilirubin, indirect bilirubin): Screening; Pre-Baseline; all visits during the treatment period; early termination; and Follow-up Week 2.
  - Lipids (total cholesterol, high-density lipoprotein [HDL] cholesterol, low-density lipoprotein [LDL] cholesterol, triglycerides): Pre-Baseline; Weeks 24 and 52; and early termination.
- Urinalysis: Pre-Baseline; Week 52; and early termination.

Clinically significant laboratory abnormalities are identified as grade 3 to 4 laboratory test results. Refer to the Zavegeptan Core SAP for laboratory tests of clinical interest for analyses, including identification of those with toxicity grades.

The following by-subject laboratory test listings are provided for the enrolled analysis set:

- Select laboratory test groups: hematology (both SI and US units)\*; serum chemistry, including LFTs (both SI and US units)\*; urinalysis (US units only)\*; pregnancy (US units only)\*; endocrinology, serology, drug screen, and miscellaneous laboratory tests (US units only). The pregnancy listing identifies positive pregnancy tests, which are defined as serum or urine pregnancy tests with either (a) “positive” character value, or (b) numeric value  $\geq 25$  U/L.
- LFT values and ratios to ULN (i.e., ALT, AST, TBL and ALP) for both US and SI units\*. The listing displays all LFT results over time for subjects with select LFT elevations (ALT or AST  $> 3$  x ULN; ALP or TBL  $> 2$  x ULN) at any time point.

- Creatine kinase (CK) elevation questionnaire.

Listings display toxicity grades and identify expired kits from the central laboratory, if applicable, and those marked with “\*” display COVID-19 visit impact code for visits impacted by COVID-19 (see Section 9.1.5.2). Refer to the Zavegeptan Core SAP for listing contents.

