#### 6.4.2.3 *Laboratory Test Changes from Baseline*

Values and changes from baseline in hematology and serum chemistry laboratory tests are tabulated descriptively as continuous variables at baseline and each scheduled visit in the on-treatment and follow-up safety analysis periods.

If a subject has multiple values in an analysis visit window in a safety analysis period, then a single value is selected using the following hierarchy as available:

- Non-missing viable value collected closest to the target date for the visit. In the case of a tie, the last non-missing viable value collected is used. If there are multiple viable values on the same date, then the following hierarchy is used as available:
  - Last central laboratory test value collected timewise with the last accession identifier.
  - Last local laboratory test value entered.

Viable laboratory test values are defined as those from (1) kits from the central laboratory that are not expired (see Section 6.4.2), or (2) local laboratory tests reported on CRFs.

- Non-missing value from an expired kit from the central laboratory collected closest to the target date for the visit. In the case of a tie, the last non-missing value collected with the last accession identifier is used.

Results are also summarized at the EOT visit with a single value in the on-treatment safety analysis period using the following hierarchy as available:

- Last non-missing viable value collected. See above for handling multiple viable values on the same date.
- Last non-missing value collected with the last accession identifier from an expired kit from the central laboratory.

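### On-treatment safety closes 7 days after the last as-needed spray, so some Week 52 hematology and non-LFT chemistry panels drop out of the primary Grade 3-4 count

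*SAP*

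**What the plan says.** SAP 7.2 sets the on-treatment safety period as "measurement date/time after the study drug start date/time through the study drug last date + 7 days"; anything later is follow-up safety. SAP 7.1 fixes the anchor: "Study drug end date/time: Latest study drug date/time", and "At the last database lock, the study drug last date is equal to the study drug end date". For a subject who has not yet exited, the last date is left undefined: "Thus, in an interim analysis, all post-baseline data are included for a subject who is still on study".

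The Protocol synopsis states: "The Week 52 (+/- 7 days) visit is the end of treatment visit". Study drug is used at migraine onset, at most once per calendar day and 8 times per 28 days (Protocol 7.2.2).

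SAP 6.4.2 gives the draws as "Hematology: Screening; Pre-Baseline; Weeks 4, 24, and 52; and early termination" and "Serum chemistry (including LFTs and lipids): Screening; Pre-Baseline; Weeks 4, 24, and 52; and early termination". There are two exceptions. LFTs are drawn at every treatment visit and at Follow-up Week 2; lipids are drawn after baseline only at Weeks 24 and 52 or early termination.

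SAP 6.4.2.1 builds the graded-laboratory table that carries the primary Grade 3-4 result from on-treatment values. It repeats that table separately for follow-up and restricts the shift tables to on-treatment values. Under SAP Table 1 the denominator is subjects with laboratory data. For the change-from-baseline tables, SAP 6.4.2.3 says: "Results are also summarized at the EOT visit with a single value in the on-treatment safety analysis period".

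**The concern.** For a drug taken on a fixed schedule, last dose plus 7 days reaches the end-of-treatment visit almost by construction. For a drug taken only during attacks it need not. A subject who still holds study drug, is still completing the diary and has not had a recent migraine looks, under this rule, like someone who has stopped.

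Classification also depends on what happens afterwards. The on-treatment period runs unbroken from first to last spray. A Week 24 panel drawn, say, 20 days after a spray is therefore on-treatment if any spray follows, while a Week 52 panel drawn 20 days after a spray is not.

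The effect falls on the sparsest laboratory data and on a component of the primary endpoint. If the Week 52 panel moves, three things follow:

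- A Grade 3-4 value first seen there is not in the primary count, although the Week 4 and Week 24 panels keep the subject in the denominator.
- The row labelled EOT can show a value from Week 24.
- Scheduled hematology and non-LFT chemistry in the follow-up table come entirely from Week 52 or early termination visits, because none is scheduled at Follow-up Week 2.

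The interim report can also treat the same panel differently from the final report, because subjects still on study at the interim have no cut-off.

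**Working it through.** **The plan's own figure.** SAP section 5 gives a one-sided 95% upper bound of 0.005 for 0 events in 600 treated subjects. The exact value is 1 − 0.05^(1/600) = 0.00498, so it reproduces. It concerns AEs in treated subjects and is not affected by this point.

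**When a panel moves.** A panel on visit day V is on-treatment only if the last spray falls on day V−7 or later. The panel moves if there was no spray on the 7 days before the visit, or on 8 days if a spray on the visit day itself can count. I show both.

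**Input that must be assumed.** The documents give no distribution of spray frequency or timing. Let r be sprays per 28 days. I take r from 2 to 8: 8 is the maximum (Protocol 7.2.2), and an average below 2 over 3 consecutive months is a discontinuation reason (Protocol 6.6).

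**Formulas for the share of Week 52 panels that move.**

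- Even spacing, interval 28/r: max(0, 1 − 7r/28) or max(0, 1 − 8r/28)
- Random timing, whole days: (1 − r/28)^7 or (1 − r/28)^8
- Random timing, continuous: exp(−r/4)

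| Model | r=2 | r=4 | r=6 | r=8 | Mean, r uniform 2-8 |
|---|---|---|---|---|---|
| Even, 7 days | 50% | 0 | 0 | 0 | 8.3% |
| Even, 8 days | 43% | 0 | 0 | 0 | 5.4% |
| Random, 7 whole days | 59.5% | 34.0% | 18.5% | 9.5% | 28.3% |
| Random, 8 whole days | 55.3% | 29.1% | 14.5% | 6.8% | 24.1% |
| Random, continuous | 60.7% | 36.8% | 22.3% | 13.5% | 31.4% |

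The means are integrals over r divided by 6:

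- Even, 7 days: (1/6)∫ from 2 to 4 of (1 − r/4) dr = 0.5/6 = 0.083.
- Even, 8 days: (1/6)∫ from 2 to 3.5 of (1 − 2r/7) dr = 0.321/6 = 0.054.
- Random, whole days: (28/8)[(26/28)^8 − (20/28)^8]/6 = 0.283, and (28/9)[(26/28)^9 − (20/28)^9]/6 = 0.241.
- Continuous: 4(e^−0.5 − e^−2)/6 = 0.314.

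If all 600 treated subjects had a Week 52 visit, 5.4% would be 32 panels and 31.4% would be 188. This only illustrates scale, since some subjects will leave early. The continuous model also ignores the limits of one spray per day and 8 per 28 days, so its 31% is the less realistic end.

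**Effect for one completer.** One of three scheduled post-baseline hematology and general chemistry panels moves, and one of two for lipids. The last scheduled on-treatment panel is then Week 24.

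**Adverse events, for comparison.** The mean treatment-phase time beyond last spray + 7 days, with r uniform over 2-8, is as follows:

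- Even spacing, with s = 28/r and (s − 7)²/(2s) when s > 7: 0.16 days, and 0.16/364 = 0.04%.
- Random timing, (28/r)exp(−r/4): 2.38 days, and 2.38/364 = 0.65%.

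**The case against.** The strongest reply is that nothing here is an error. The protocol's endpoints are on-treatment endpoints, SAP 3.2 declares a while-on-treatment strategy for safety, and last dose plus a fixed lag is a normal way to apply it. That stands: the rule contradicts nothing in the documents and should remain the primary window.

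It is also true that the results stay visible. A displaced Grade 3-4 value appears in the follow-up graded-laboratory table (SAP 6.4.2.1) and in the by-subject hematology and chemistry listings, which show toxicity grades for the enrolled set (SAP 6.4.2). The listings let a reader resolve, subject by subject, any double counting from adding the two tables. Clinically significant results should also be recorded as AEs (Protocol 8.3.2).

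A reader might infer more than the documents support:

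- **That safety data disappear.** They do not. They are relabelled.
- **That no combined table exists anywhere.** This SAP describes none for laboratory grades. The Core SAP and the mock TLF document, to which it defers for details, were not available.
- **That AE and SAE counts are materially low.** The treatment time involved is at most 0.65% under the models above. Follow-up AE and SAE tables and follow-up SAE narratives are already planned.
- **That the precision stated in the sample size section is weakened.** Affected subjects stay in the denominator, and no planned analysis counts only retained Week 52 panels.
- **That the rule leaves the second half of the year unmonitored.** The protocol schedules no hematology or non-LFT chemistry between Weeks 24 and 52 for anyone. Only the Week 52 panel itself is at issue.
- **That every early-termination panel is misplaced.** Where a subject had already stopped the drug, follow-up is the proper label.

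What survives is narrower. In subjects still in the treatment phase, the primary laboratory count can miss a Week 52 result, and the EOT row can carry an older value under that label.

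**Conclusion.** The point holds as a minor one. The mechanism follows directly from SAP 7.1 and 7.2. Its consequence is confined to hematology and non-LFT chemistry; LFTs are drawn at every treatment visit and are little affected.

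The size is uncertain. With use uniform over 2-8 sprays per 28 days, about 5-8% of Week 52 panels move under even spacing and 24-31% under random timing. Evenly spaced use at 4 or more per 28 days gives 0. Infrequent users and visits delayed for COVID-19 reasons (Protocol 4.3.5) would raise the share. These are model figures. The trial's own interval from last spray to the end-of-treatment visit would settle the matter.

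How many Grade 3-4 results would move cannot be estimated, because the documents give no rate for them. The plan is defensible as written, and the change below is a cheap improvement to how the primary laboratory result is read.

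**What to change.** Leave last spray + 7 days as the primary window and make these additions to the SAP:

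1. One supplementary worst-grade table showing Grade 3-4, with its grade shift table, for hematology and non-LFT chemistry. It runs from first dose through the later of (a) last spray + 7 days and (b) the Week 52/Early Termination visit. Subjects without such a visit keep (a).
2. In the laboratory change-from-baseline tables, a second EOT row that uses the actual Week 52/Early Termination value.
3. A tabulation of days from last spray to the end-of-treatment visit, so a reader can see how many panels the window excludes.
4. The same outputs in the interim and final CSRs, so that the two reports can be compared on one definition.

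No new AE or SAE tables are needed. The cost is SAP wording and a few programmed outputs. The spray dates already come from the eDiary and its medication reconciliation form, and the visit dates from the Visit Date CRFs (SAP 7.1). The downside is that the supplementary tables will include some drug-free days, including days after discontinuation in early terminators and days of visit delay. For that reason they should stay supplementary, outside the while-on-treatment primary analysis.
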